4.4 Duration of Therapy

In the absence of treatment delays due to adverse event(s), treatment may continue until one of the following criteria applies:

- Lack of objective response after 2 cycles of therapy (3 cycles if there is dose escalation to 50 mg BID after cycle 1) unless INCB018424 is considered to be of clinical benefit to the patient
- Intercurrent illness that prevents further administration of treatment
- Unacceptable adverse event(s)
- Patient decides to withdraw from the study, or
- General or specific changes in the patient's condition render the patient unacceptable for further treatment in the judgment of the investigator.

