4. TREATMENT PLAN

4.1 Dose of INCB018424 and Treatment Cycle

This is a phase II study of oral INCB018424 in patients with relapsed/refractory AML, ALL, and MDS (including CMML), and blast phase or tyrosine kinase refractory CML. The starting dose of INCB018424 will be 25 mg po twice daily, which has been determined to be the maximum tolerated dose in patients with myelofibrosis with myeloid metaplasia and a dose that is tolerated for ten days in normal human volunteers.

INCB018424 will be administered orally at a dose of 25 mg BID for 7 days each week for 4 weeks (cycle number 1). Patients will be evaluated after 1 full cycle of therapy (28 days) for response. Responding patients or patients with stable disease will be allowed to continue on study at a dose of 25 mg INCB018424 BID until progression. The response assessment for the purpose of study statistical evaluation will be after two cycles (8 weeks) of therapy. Patients with progressive disease, based on clinical and laboratory evaluation, will, at the discretion of the Investigator, either be removed from the study or, as long as the 25 mg BID dose has been well tolerated, dose escalated to 50 mg INCB018424 BID. In instances of dose escalation to 50mg BID, patients will be evaluated after

1 full cycle of therapy (28 days) for response and toxicity. At that point, patients with continued progressive disease, based on clinical and laboratory evaluation, will be removed from the study. In instances of dose escalation, the response assessment for the purpose of study statistical evaluation will be after two cycles (8 weeks) of therapy at the 50 mg BID dose.

Patients with chronic phase CML who have failed at least 2 prior tyrosine kinase inhibitors and do not have a standard transplant option will be assessed for response after 3 months of therapy in the absence of loss of disease control and they may continue therapy if they demonstrate any clinical benefit. Patients with chronic phase CML will not be allowed to have the dose escalation as this population has less of a life-threatening disease situation.

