9.4.3 Time to Treatment Failure

"Time to Treatment Failure" is defined as the period of time from the date of first study drug administration to the date of withdrawal from the study for any reason other than study closure.

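### Section 4.4 can end chronic-phase CML treatment for non-response at day 56, before the 3-month assessment in section 4.1 and the first scheduled on-treatment marrow at day 85

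*Combined protocol and SAP*

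**What the plan says.** **Section 4.4, Duration of Therapy.** One listed reason to end treatment is "Lack of objective response after 2 cycles of therapy". The same bullet allows 3 cycles when the dose is escalated after cycle 1, and it carries an exception: "unless INCB018424 is considered to be of clinical benefit to the patient". Clinical benefit is not defined. Chronic-phase CML is not mentioned, and section 4.1 bars that group from escalation, so the 3-cycle allowance cannot apply to it.

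**Section 4.1, general rule.** After the cycle 1 evaluation, "Responding patients or patients with stable disease will be allowed to continue on study at a dose of 25 mg INCB018424 BID until progression". On timing: "The response assessment for the purpose of study statistical evaluation will be after two cycles (8 weeks) of therapy".

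**Section 4.1, chronic-phase CML.** These patients "will be assessed for response after 3 months of therapy in the absence of loss of disease control", and may then stay on treatment if they show any clinical benefit.

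**Marrow and cytogenetics.** Section 5.2 (footnote i) and sections 7.3 and 7.3.2 schedule these at screening, at the start of Cycles 4 and 7, and every sixth cycle after that. The marrow window is ±7 days.

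**Section 6.2.** Complete haematologic response requires a marrow blast criterion. No evidence of leukaemia shares it, and minor haematologic response has its own marrow blast criteria. Cytogenetic response rests on the cytogenetic sample.

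**Section 9.4.** Time to Treatment Failure runs to the "date of withdrawal from the study for any reason other than study closure". Survival, as written, ends at death or at withdrawal from the study.

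**The concern.** For chronic-phase CML the protocol sets two clocks. The non-response criterion falls due at the end of cycle 2, while the response assessment for the same patients is set at 3 months. The procedures that could show a response are scheduled later than the point at which its absence ends treatment. A patient who would have responded by Cycle 4 could leave without the measurement. Section 9.1.1 expands a disease category from 10 to 30 patients on the strength of at least one response, so a response missed in this way bears on a design decision as well as on the final estimate.

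The second, smaller matter is stable disease. Section 9.5.2 lists it separately from complete and partial response, so a stable patient lacks an objective response. Section 4.1 lets that patient continue to progression. Section 4.4 lets the patient continue only if benefit is judged to be present, and does not say whether stability is enough. Endpoints timed to withdrawal then partly reflect how that judgement is made.

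**Working it through.** **The plan's own figures.** Section 9.1.1 states 80% power with 10 patients per category, a 0% null rate and a 15% target. The probability of at least one response in 10 is 1 − 0.85^10 = 0.803. The stated half-width of 0.13 at n = 30 is 1.96 × √(0.15 × 0.85 / 30) = 0.128. Both reproduce and neither is in dispute.

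**Timing for chronic-phase CML** (28-day cycles, sections 4.1, 4.4 and 5.2)

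- Section 4.4 criterion due: 2 × 28 = day 56.
- Section 4.1 assessment at 3 months: day 84 (3 × 28) to about day 91, which is 28 to 35 days later.
- First scheduled on-treatment marrow and cytogenetics: Cycle 4 Day 1 = 3 × 28 + 1 = day 85.
- Gap: 85 − 56 = 29 days. With the ±7-day marrow window it is 22 to 36 days, holding the cycle 2 point at day 56.

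**What can be documented at day 56.** Every haematologic category in section 6.2.1 needs marrow blasts, and section 6.2.2 needs cytogenetics. Neither is scheduled between screening and Cycle 4. The end-of-study visit includes a response assessment but no scheduled marrow. Section 6.2.3 defines molecular response, but the study calendar lists no BCR-ABL sample. Taking objective response to mean a section 6.2 category (section 4.4 does not define it), the scheduled procedures cannot show one by day 56. Read literally, every chronic-phase patient then meets the non-response criterion and depends on the exception.

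**Possible effect on the 10-patient decision.** Let k of the first 10 CML patients be stopped before their response can be documented. The documents do not give k. Assuming a true rate of 15% in every patient and no response recorded in those k, the probability of at least one observed response is 1 − 0.85^(10 − k):

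| k | Probability |
|---|---|
| 0 | 0.803 |
| 1 | 0.768 |
| 2 | 0.728 |
| 5 | 0.556 |

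If the exception keeps all such patients on treatment, k = 0 and nothing is lost.

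**Stable disease and Time to Treatment Failure.** Let r be the share responding at week 8, s the share stable without response, and g the fraction of stable patients given the exception. All others are taken to have failed already. Freedom from treatment failure just after week 8 is r + g × s. The value r = 15% is the design target; s is not in the documents, and 10-50% is assumed.

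- g = 0: 15%, or 4.5 of 30 patients.
- g = 1: 15% + 10% = 25% up to 15% + 50% = 65%, or 7.5 to 19.5 of 30.

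With g = 1, sections 4.1 and 4.4 give the same result.

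**The case against.** The strongest reply is that section 4.4 is not an unconditional stop. Its exception recurs as the continuation test elsewhere, including section 4.1 for chronic-phase CML, and the chronic-phase paragraph can be read as the specific rule that overrides the general one. On that reading nobody is removed early. The reading is reasonable, but the text does not state it: section 4.4 makes a timing allowance for escalation and makes none here.

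Several stronger readings are tempting, and the documents do not support them.

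- *Sections 4.1 and 4.4 contradict each other outright on stable disease.* They do not. A stable patient judged to benefit continues under both. The fault is an undefined term.
- *Chronic-phase CML is assessed only at 3 months.* Section 5.2 (footnote d) and section 6 require assessments over the first three cycles with no chronic-phase exemption. What is missing is scheduled marrow and cytogenetics before Cycle 4.
- *All withdrawal-based endpoints are affected.* Time to Progression counts withdrawal only for progressive disease, alongside death. Time to Treatment Failure counts other withdrawals by design, is shown only as Kaplan-Meier curves, and is not among the efficacy variables in section 9.2.
- *A patient stopped at week 8 must count as a non-responder.* Section 9.5.2 has an unknown category, and the plan does not say how it enters the denominator.

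It is also true that the first on-treatment marrow comes at Cycle 4 for every disease. That mismatch with the 8-week assessment is a separate matter and would remain after this one is settled. What is particular to chronic-phase CML is that section 4.1 itself sets the later assessment, which section 4.4 ignores.

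**Conclusion.** The chronic-phase CML mismatch stands. As written, section 4.4 can end treatment 22 to 36 days before the scheduled procedures can document a haematologic or cytogenetic response, with only a discretionary and undefined exception to prevent it. The direction is towards fewer observed responses in the CML category. The size cannot be derived from the documents, because neither the number of chronic-phase patients nor the use of the exception is given. The figures for k above are illustrations that assume a 15% rate and no response recorded in patients stopped early.

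The stable-disease point stands as an ambiguity. Time to Treatment Failure, and Survival as defined, depend on how the exception is applied. Under the assumed shares the difference just after week 8 runs from none, if every stable patient is judged to benefit, to 10-50 percentage points, if none is. The 8-week assessment point for the other disease groups and the sample-size calculation are not affected.

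**What to change.** Sections 4.1 and 4.4 must be reconciled on two points:

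1. The timing of the section 4.4 non-response criterion and the timing of the chronic-phase CML response assessment in section 4.1 should agree.
2. It should be clear whether stable disease meets the clinical-benefit exception in section 4.4.

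Which clinical rule is adopted is for the investigators and sponsor, and no view is taken here. Once it is settled, one sentence in section 9.5.2 should say how a patient whose treatment ends before the planned response assessment is classified and whether that patient stays in the response denominator.

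The cost is protocol wording. Aligning the text does not in itself require new visits or samples or a change to the sample size.

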4.5 Dosing Delays/Dose Modifications

Dose Adjustments

The dose of INCB018424 will be adjusted according to the guidelines shown in the following tables for INCB018424 - related clinically significant toxicity. If a toxicity is not covered in the table, doses may be reduced or held at the discretion of the investigator for the patient's safety. Dose adjustments for hematological toxicity are based on the blood counts obtained in preparation for the day of treatment i.e. CBC within 3 days of Day 1 of that cycle.

Patients will be withdrawn from the study if they fail to recover to CTC AE grade 0 to 2 (or within 1 grade of starting values for pre-existing laboratory abnormalities) from a treatment-related toxicity within 2 weeks (leading to treatment delay of > 2 weeks) unless the investigator feels that the patient should remain in the study because of evidence that the patient is/may continue deriving benefit from continuing study treatment.

Patients with toxicities that are manageable with supportive therapy may not require dose reductions. Patients requiring greater than 1 dose reduction of INCB018424 should be withdrawn from the study, unless INCB018424 is considered to be of clinical benefit to the patient.

Dose modification for neutropenia and thrombocytopenia grade 4 persisting beyond 2 weeks of therapy is allowed if the treating physician believes them to be related to the treatment and not the underlying disease. The dose can be held until the AE is to grade 2 or lower; then INCB018424 will be restarted at 15 mg BID or an equivalent dose given daily. Alternatively, at the discretion

of the treating physician, the dose may be reduced to 15 mg BID without holding the drug if the treating physician believes that the cytopenia is related to a combined effect of the drug and uncontrolled disease.

Dosing for INCB018424- Related Toxicities

NCI CTC AE Grade

Grade 0-2 non-hematological toxicity

Grade 3-4 clinically significant nonhematological toxicity

INCB018424

No dose reduction.

Grade 2 toxicities that are persistent and intolerable (e.g. stomatitis) can result in dose delays or dose reduction to 15 mg

BID in Cycle 2 or beyond.

Hold until recover to NCI CTC AE grade 0-2 If recovery occurs within 2 weeks after treatment has been held, dose should be reduced to 10 mg or 15 mg BID. At the discretion of the investigator and if the patient is considered to be benefiting, the patient will receive an intermittent dose schedule, alternating treatment periods and recovery periods at the 25 mg BID dose. i.e alterations to the dose and schedule that is thought to be beneficial to the patient in the responding patients may be allowed after discussion with IRB, FDA and the PI.

4.6 Concomitant medications

INCB018424 is predominantly metabolized by CYP3A4.

The potential for INCB018124 to inhibit or induce human Cytochrome P450 enzymes has been extensively investigated. The available data suggests that the potential for INCB018124 to cause clinical drug interaction via CYP inhibition is low. Furthermore, in vitro data suggest that the potential for INCB018124 to induce CYP3A4 is also low. Therefore there is little potential to interact with other drugs.

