- J. In patients who are receiving medications known to be inhibitors or inducers of CYP3A4 every effort will be made to change these medications to acceptable alternatives. If this is not safely possible, patients will be excluded from participation in the study. If a patient is already on the study, must be started on a CYP3A4 inhibitor, and is demonstrating benefit from the study, they will be seen twice weekly in the first cycle and weekly in the subsequent cycles for toxicity evaluation and their dose will be modified according to the table in section 4.5 in the event of a toxicity thought to be related to the study drug. A list of CYP3A4 inducers and inhibitors is provided in Appendix I.

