4.3 Supportive Care Guidelines

Supportive measures including erythropoietin, analgesics, blood transfusions, antimicrobials, and hematopoietic colony stimulating factors for treatment of cytopenias are permitted.

Prophylactic use of hematopoietic colony stimulating factors is not permitted.

Other chemotherapy, investigational cytotoxic agents, radiation, or biologic therapy is prohibited while the patient is on study with the following exceptions during cycle 1: During the first 7 days of study only, patients may receive leukaphereses (not more than three procedures per week and not more than five procedures in total to control elevated blast and/or platelet counts and/or hydroxyurea (up to a maximum of 5 gm/day) for a maximum of 14 days. Intrathecal chemotherapy to treat isolated CNS involvement of leukemia is allowable.

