- d. Overall response assessments are required on Day 1 of Cycles 2, 3, and 4 and then every 3 months thereafter. If the dose of INCB018424 is escalated to 50 mg BID after cycle 1, then overall response assessments are required on Day 1 of Cycles 3, 4, and 5 and then every 3 months thereafter.
- e. ECOG performance criteria must be 0, 1 or 2 at screening. ECOG assessment is required on Day 1 of 2nd and 3rd cycles and thereafter every scheduled subsequent visit on Day 1.
- f. All medications received within 30 days prior to the Screening Visit are to be recorded. Reassessments will be done weekly at the local physician's office during 1st cycle of therapy and then every 4 weeks during 2nd and 3rd cycles and thereafter every 3 months during scheduled visits.
- g. Serum chemistry (Sodium, potassium, chloride, CO₂, blood urea nitrogen, creatinine, glucose, calcium, phosphate, magnesium, AST or ALT, total bilirubin, alkaline phosphatase, total protein, albumin, uric acid, lactic dehydrogenase) is required every week during the 1st cycle and every two weeks during Cycles 2 and 3, and at each scheduled subsequent visit. Urinalysis is required only at screening and at the end of study visit. Hepatitis serology and HIV laboratory test will be performed only during the Screening Visit if there are no results available from past 3 months. A pregnancy test will be obtained at screening. Urine pregnancy test will then be performed if there is a suspicion of pregnancy. A serum pregnancy test will be performed to confirm positive results obtained from a urine test. FSH test will only be performed on females who have been amenorrheic for >1 year, and if levels are elevated no further pregnancy testing is required for these female patients.
- h. Complete blood count (CBC) including absolute neutrophil count and platelet count are required weekly for Cycle 1, 2 and 3 and every two weeks for subsequent visits.

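### Section 4.6 concludes there is little interaction potential although CYP3A4 clears the drug, and from Cycle 2 a CYP3A4 inhibitor started outside the study team can go unrecognised for 4 weeks to 3 months

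*Combined protocol and SAP*

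**What the plan says.** Section 4.6 (Concomitant medications) opens with "INCB018424 is predominantly metabolized by CYP3A4". The evidence that follows concerns only the drug's own action on CYP enzymes: "The available data suggests that the potential for INCB018124 to cause clinical drug interaction via CYP inhibition is low", with a similar statement that induction of CYP3A4 is unlikely. It closes with "Therefore there is little potential to interact with other drugs". It does not mention other drugs changing the study drug's exposure, and it refers neither to 3.2 J nor to Appendix I. (The compound code printed in those sentences differs from the study drug's code and should be corrected or explained.)

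Criterion 3.2 J takes the opposite direction of interaction seriously. At entry, inhibitors and inducers of CYP3A4 are to be changed, and "If this is not safely possible, patients will be excluded from participation in the study". For a patient already on study who is benefiting and has to start an inhibitor, "they will be seen twice weekly in the first cycle and weekly in the subsequent cycles for toxicity evaluation".

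Section 4.3 permits "Supportive measures including erythropoietin, analgesics, blood transfusions, antimicrobials" and growth factors for cytopenias, with no pointer to J.

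Section 5.2, footnote f, sets medication review weekly in Cycle 1, "then every 4 weeks during 2nd and 3rd cycles and thereafter every 3 months during scheduled visits". Footnote b limits medication history to screening. The monthly contact in 5.2.4 covers general condition, new or worse symptoms, adherence to drug and laboratory schedule, and patient questions. New medications are not on the list.

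**The concern.** Whether a drug changes the metabolism of others and whether others change its metabolism are separate questions. Section 4.6 presents evidence on the first and words its conclusion to cover both. Someone who consults the concomitant-medication section during treatment is told that interactions are of little concern, while the rule that says otherwise sits among the exclusion criteria. Antimicrobial use is foreseeable, because 8.1 treats fever and infection as expected, and 4.1 places much of the routine follow-up with local physicians.

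J also depends on the study team knowing that an inhibitor has been started. If they do not know, the patient stays on the ordinary schedule. Any resulting grade 3 or 4 toxicity that is judged drug-related and lasts more than 2 weeks counts toward the stopping limits in 4.1 and 9.1.1 (30% in cohort I, 15% in cohort II). Under 9.3.1, an event with no stated relationship is counted as treatment-related. Toxicity partly due to an interaction could therefore be read as toxicity of the nominal dose. PK sampling would not reveal it later, because the last scheduled sample is pre-dose on Day 1 of Cycle 3.

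**Working it through.** The plan gives no figure to reproduce here. The check has a textual part and a scheduling part.

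**Text.** The premise in 4.6 is that CYP3A4 clears the drug. The evidence is that the drug has low potential to inhibit or induce CYPs. What follows is low potential to alter other CYP-cleared drugs. Nothing cited bears on an inhibitor or inducer altering this drug, and the premise points towards that possibility. J acts on it.

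**Schedule.** Inputs:
- T, the interval between medication reviews (5.2, footnote f): 7 days in Cycle 1; 28 days in Cycles 2 and 3; 3 months from Cycle 4, taken as 84 days (three 28-day cycles) to 91 days.
- m, the interval between J's visits (3.2 J): about 3.5 days when twice weekly, 7 days when weekly.
- d, the length of an inhibitor course. The documents give none, so 7 to 28 days is an assumption.

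Formulas, for a start date uniform over the interval and not otherwise reported: worst lag = T; mean lag = T/2; J visits due in one interval = T/m; chance that the course begins and ends between two reviews = max(0, (T − d)/T).

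| Period | T (days) | Mean lag (days) | J visits in one interval |
|---|---|---|---|
| Cycle 1 | 7 | 3.5 | 7/3.5 = 2 |
| Cycles 2 and 3 | 28 | 14 | 28/7 = 4 |
| Cycle 4 onward | 84 to 91 | 42 to 45.5 | 84/7 = 12 to 91/7 = 13 |

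Chance that a course is over before the next review:
- Cycles 2 and 3: d = 7, 21/28 = 75%; d = 14, 14/28 = 50%; d = 21, 7/28 = 25%.
- Cycle 4 onward: d = 7, 77/84 to 84/91 = 92%; d = 14, 70/84 to 77/91 = 83% to 85%; d = 28, 56/84 to 63/91 = 67% to 69%.

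In those cases J's visits could not have been held while the inhibitor was being taken, even if the course were recorded afterwards.

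If the monthly contact did capture new medications (T about 30 days), the worst lag from Cycle 4 would fall to about 30 days, or 30/7 = about 4 weekly visits. A 14-day course would then be missed while running with chance 16/30 = 53%. Visit windows are ignored throughout; they move these figures by days.

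**The case against.** The best defence of 4.6 is that its last sentence closes a passage about the drug's effect on CYP enzymes and should be read in that scope. The section gives no permission, and J remains the only operative rule. This stands in part: 4.6 does not override J, and a reader who infers that the protocol allows inhibitors freely goes further than the text. But the sentence is unqualified and no cross-reference corrects it.

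On scheduling, four points stand. Cycle 1 review is already weekly, so the gap there is small. A start made with the study team's knowledge triggers J at once, so the gap concerns only unreported outside prescriptions. Blood counts are weekly in Cycles 1 to 3 and two-weekly after, the investigator reviews results, and some patients may be seen monthly for drug supply (4.1); these may expose toxicity but do not name its cause. Finally, Appendix I and the consent text are not available here, so existing instructions to patients about new medicines cannot be judged.

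Two stronger readings are tempting. The first is that J's twice-weekly tier can hardly ever apply, because J requires benefit while 4.1 says "Patients will be evaluated after 1 full cycle of therapy (28 days) for response". The documents do not support this. Section 4.4 distinguishes clinical benefit from objective response, and benefit could be judged at the weekly Cycle 1 visits. J's mention of the first cycle may also mean the first cycle on the inhibitor. That is an ambiguity, not a demonstrated failure.

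The second is that an inhibitor would bring patients to the 50 mg BID exposure at which dosing was halted after two of four patients (Section 2.2.3). The documents give no exposure ratio, that experience was in myelofibrosis, and 4.1 itself allows escalation to 50 mg BID except in chronic phase CML.

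**Conclusion.** The point holds in two parts. First, the conclusion of 4.6 does not follow from its evidence and conflicts with 3.2 J; this rests on the text alone. Second, from Cycle 2 onward the scheduled medication review is too infrequent to bring J into effect for an inhibitor started outside the study team. The possible delay is up to about 28 days in Cycles 2 and 3, and about 3 months from Cycle 4, against the weekly visits J sets for patients who are benefiting.

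The delays assume that nobody reports the start between reviews. The percentages also assume a uniform start date and the stated course lengths. How often inhibitors would be started, and how far exposure would rise, cannot be derived from the documents, so no count of affected patients or toxicities is claimed. This is a correction the sponsor should make for patient safety and for clean attribution of toxicity. It does not affect the sample size or the response analysis.

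**What to change.** - Limit the last sentence of 4.6 to the drug's effect on other drugs.
- Cross-refer 4.6, and the antimicrobials entry in 4.3, to 3.2 J and Appendix I.
- Add a question on new medications to the monthly contact in 5.2.4.
- Instruct patients and local physicians to tell the study team of any new medication when it is started. This also covers Cycles 2 and 3, where 5.2.2.2 schedules local laboratory draws but no routine study-team contact between visits.
- Have the sponsor reconcile 3.2 J, 4.3 and 4.6, and state whether the first cycle in J means study Cycle 1 or the first cycle on the inhibitor. No monitoring or dosing rule is proposed here.

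The cost is wording changes, one question at a contact already scheduled from Cycle 4, and one instruction. It does not close the gap fully: if a start is not reported, a lag of up to about a month remains (28 days in Cycles 2 and 3, about 30 days later).
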